4.3 Secondary Objectives

To compare the three intervention alternatives (GEN, E-GEN, and TAU) with respect to:

- MDD symptoms;
- Changes to initial prescribing based on availability of pharmacogenomics data;
- Response rates to psychotropic medication;
- Remission rates;
- Time to response/remission;
- Medication side effects, including weight gain;
- Health-related quality of life;
- Physician's attitude and experience to DNA testing;
- Healthcare resource utilization and productivity losses;
- Total estimated healthcare costs associated with the treatment and management of patients;
- Cost-effectiveness of the GEN and E-GEN technology relative to TAU

5.0 TRIAL DESIGN

This study is designed as a three-arm multi-centre, double-blind (participants and raters), randomized controlled trial to compare the clinical and economic outcomes of GEN, E-GEN and TAU for patients suffering from a MDD and having had – within the current episode - an inadequate response to at least one psychotropic medication included in GEN. Participants will be randomized in a 1:1:1 ratio to each of the three treatment arms.

6.0 METHODS: PARTICIPANTS, INTERVENTIONS, AND OUTCOMES

6.1 Study Setting

This study will be conducted in an outpatient setting. Participants will be recruited from academic and community hospital outpatient clinics, family health teams and primary health care clinics in Ontario.

6.2 Eligibility Criteria

Patients meeting the following criteria will be approached for study enrollment:

6.2.1 Inclusion Criteria

1. 18 years of age or older;
2. Suffer from a Major Depressive Episode meeting Diagnostic and Statistical Manual of Mental Disorders, Fourth Edition, Text Revision (DSM-IV-TR) criteria;
3. Have had an inadequate response within the current episode to at least one psychotropic treatment (listed in Appendix I). Inadequate response is defined as inadequate efficacy after 6 weeks of a psychotropic treatment or discontinuation of a psychotropic treatment due to adverse events (AEs) or intolerability;
4. Have each a screening and baseline score on the 16-item Clinician Quick Inventory of Depressive Symptomatology (QIDS-C₁₆) and 16-item Self-Report Quick Inventory of Depressive Symptomatology (QIDS-SR₁₆) rating scales ≥ 11 ;
5. Be able to understand the requirements of the study and provide written informed consent to participate in this study;
6. Agree to abide by the study protocol and its restrictions and be able to complete all aspects of the study, including all visits and tests.

6.2.2 Exclusion Criteria

Any of the following conditions are cause for exclusion from the study:

1. Patients posing a serious suicidal risk and/or in need of immediate hospitalization as judged by the Investigator;
2. Patients with a diagnosis of Bipolar I or II disorder;
3. Patients with a current Axis I diagnosis of:
 - Delirium
 - Dementia
 - Amnestic and/or other cognitive disorder
 - Schizophrenia or other psychotic disorder;
4. Patients having experienced hallucinations, delusions, or any psychotic symptomatology within the current depressive episode or during prior depressive episodes;
5. Patient is currently in an inpatient facility;
6. Patients with a history of hypothyroidism unless taking a stable dose of thyroid medication and asymptomatic or euthyroid for at least 6 months;

7. Patients who meet DSM-IV-TR criteria for any significant current substance use disorder;
8. Patients with:
 - hepatic insufficiency (three times the upper limit of normal (ULN) for aspartate aminotransferase (AST) and/or alanine aminotransferase (ALT)); liver transplant recipient; cirrhosis of the liver;
 - malignancy (except basal cell carcinoma) and/or chemotherapy within 1 year prior to screening; malignancy more than 1 year prior to screening must have been local and without metastasis and/or recurrence, and if treated with chemotherapy, without nervous system complications;
 - significant unstable medical condition or life threatening disease with anticipated survival of less than 6 months;
 - need for therapies that may obscure the results of treatment and/or of the study;
9. Participation in another clinical trial within 30 days of the screening visit;
10. Anticipated inability to attend scheduled study visits;
11. Patients who in the judgment of the Investigator may be unreliable or uncooperative with the evaluation procedure outlined in this protocol;
12. Patients with a history of prior pharmacogenomic testing;
13. Any change in psychotropic medication (including change in dosage) between screening and baseline;
14. Patients currently receiving electroconvulsive therapy (ECT), deep brain stimulation (DBS) or transcranial magnetic stimulation (TMS) treatments, or currently scheduled to receive maintenance treatments of ECT, DBS, or TMS during the course of the study;
15. Patients who self-report to be pregnant or lactating;
16. Patients with a history of gastric bypass surgery

7.0 INTERVENTIONS

7.1 Interventions

7.1.1 GeneSight Psychotropic (GEN)

Patients randomized to the GEN group will have buccal swabs of their cheeks taken by the clinician and mailed to the Assurex Health Ltd. (ARx) pharmacogenomics lab in a

secure envelope labeled with a unique identifier to ensure accuracy and validity. Once received, the pharmacogenomic laboratory will analyze the sample and determine the patient's genotypes and corresponding phenotypes for each of the genes tested on the GEN panel. These phenotypes will provide a clear picture of how functional each gene is with respect to drug metabolism (for CYP450 genes) and/or drug response (for neurotransmitter transporter and receptor genes).

After laboratory testing is complete and phenotypes are assigned, GEN technology categorizes the green, yellow, or red status of each drug and which footnote(s) will accompany each drug. This is accomplished by integrating the genetic data with the pharmacology for each medication on the GEN panel (see Appendix I), and incorporating data gleaned from Health Canada-approved labels and published literature.

Within three days of sample receipt at the laboratory, results are returned via the GeneSight clinician portal to the treating clinicians in the form of an interpretive report that categorizes medications into three independent bins titled "Use as Directed", the Green Bin, "Use With Caution", the Yellow Bin, and "Use with Increased Caution And With More Frequent Monitoring", the Red Bin. Medications in the Green Bin are least likely to be affected by genetic polymorphisms identified in the tested individual. Medications in the Yellow Bin are at risk for gene-drug interactions that may necessitate alternative dosing or medication selection. Medications in the Red Bin are at higher risk for a gene-drug interaction that may necessitate alternative dosing or medication selection. Guided by these results, the treating physician may decide to modify a participant's psychotropic medication selection, dose, dose regimen and/or number of medications.

7.1.2 Enhanced GeneSight Psychotropic (E-GEN)

All procedures for patients randomized to the E-GEN arm will be the same as for patients randomized to the GEN arm except that for E-GEN, the pharmacogenomic laboratory will also analyze each patient's genotypes and corresponding phenotypes for the 7 CAMH markers for AIWG. The treating clinicians will receive an interpretive report that reflects all of the E-GEN genes.

Guided by the results from E-GEN, the treating physician may decide to modify a participant's psychotropic medication, in terms of type of medication, dose, dose regimen and/or number of medications.

7.1.3 Treatment as Usual (TAU)

Patients randomized to the TAU arm will also have their DNA collected and a pharmacogenomics-based interpretive report will be generated using GEN testing. However, this report will not be shared with the treating clinicians until up to 28 days prior to the completion at 12 months of the study at which point the report will be provided to

the participant by the treating clinician. Therefore, patients in this arm will receive clinical treatment as usual, without the use or knowledge of genotyping results by their treating clinicians.

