1.3 Interventions and Duration

Patient DNA will be collected for all participants and measured for variations in drug target genes and in drug metabolizing genes. Subsequently, recommendations for optimal choices and dose adjustments for the 33 most commonly prescribed antidepressant and antipsychotic medications will be provided to participants randomized to the GEN arm. This pharmacogenomics-based interpretive report will be provided to treating clinicians of patients in the GEN arm of the study, allowing clinicians to use the report to support their treatment decisions.

The E-GEN test incorporates into the existing GEN product new markers patented by CAMH and licensed by Assurex that are predictive of side effect of antipsychotic-induced weight gain (AIWG). The pharmacogenomics-based interpretive report from E-GEN will also be provided to treating clinicians of patients in the E-GEN arm of the study, allowing clinicians to use the report to support their treatment decisions.

Participants randomized to the TAU arm will also require collection of patient DNA. A pharmacogenomics-based interpretive report will again be generated from GEN, however, this report is not provided to the treating clinician until up to 28 days prior to the completion at 12 months of the study at which point the report will be provided to the participant. Therefore, patients in this arm will receive clinical treatment as usual, without the use or knowledge of pharmacogenetics results by their treating clinicians.

Research evaluation visits for all three arms will be completed at baseline, 4, 8 and 12 weeks. To capture long-term information, including comparison between GEN and E-GEN, and each test with TAU, follow-up will also be conducted at 6, 9, and 12 months. The information collected at months 6 and 9 will be by telephone interviews while participants will return for a physician visit at month 12.

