7.2 Modifications

At any time point, clinicians can modify a participant's medication based on their clinical judgment. Any switch or change in medications will be recorded on the CRF accordingly.

Women of childbearing age are advised to use a method of birth control during the course of the study. If they intend to get pregnant during the course of the study, then they should advise their primary care physician and/or psychiatrist to ensure that the pharmacotherapy being prescribed can be assessed for safety in pregnancy.

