8.2.3 Economic Outcome Measures

i. Healthcare Resource Utilization and Productivity Losses

Resource utilization and productivity losses incurred by GEN, E-GEN and TAU patients will be captured throughout the study. Information to be collected includes: physician visits (general practitioners, psychiatric, and other specialties), hospital utilization (psychiatric and non-psychiatric), emergency department visits (psychiatric and non-psychiatric institutions), medication use (antidepressants, antipsychotics, and other medications), and laboratory tests. For patients employed at the beginning of the study, productivity losses will be captured. This includes absenteeism (the number of days out of work) and number of disability claims (both short and long term) filed.

Participants will complete an economic questionnaire to capture healthcare resource utilization and productivity losses. Since participants may differ in terms of their baseline resource utilization, the questionnaire will be administered at baseline to document historical resource utilization, over the 3 months preceding, the intervention. Appropriate unit costs for Ontario will then be assigned to the data collected in order to provide an indication of the relative costs associated with receiving GEN, E-GEN and TAU.

Data on patient health care resource utilization will also be collected by the Institute for Clinical Evaluative Sciences (ICES). ICES is a research institute in Ontario that is a secure and confidential repository for publicly-funded administrative health data. Data on physician visits, hospitalizations, emergency department visits, and drug costs covered by the Ontario Drug Benefits (ODB) program are available for all Ontario residents and costs are accessible at the individual level through use of an encrypted health card number. Primary data collected from the study will also be linked via health card number, encrypted at ICES, to the ICES administrative databases for patients who had consented to data linkage. As before, costs associated with health services utilization will be based on utilization described above, with standard unit costs for Ontario as a multiplier.

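### TAU clinicians may receive the GEN report up to 28 days before 12-month completion, so Month 12 is not assured to be unguided usual care

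*Protocol*

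**What the plan says.** Protocol 7.1.3 (TAU) states that "this report will not be shared with the treating clinicians until up to 28 days prior to the completion at 12 months". The synopsis (1.3) has the same rule: "this report is not provided to the treating clinician until up to 28 days prior to the completion at 12 months". Section 1.3 continues "at which point the report will be provided to the participant", and 7.1.3 adds that the treating clinician does this. Section 7.1.3 then concludes that TAU patients are treated "without the use or knowledge of genotyping results by their treating clinicians", with no exception for the last weeks.

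Other sections bear on what can happen in that window:

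- **Treatment changes and contacts.** Section 7.2 says "At any time point, clinicians can modify" medication. Section 9.9 lets investigators see participants whenever clinical management calls for it.
- **Participant disclosure.** Section 9.7 has disclosure documented at the Month 12 visit but does not place it before or after that visit's assessments. Section 13.0 requires participants and assessing staff to be blinded.
- **Physician questionnaire.** The 12-month part of the PIP-FQ (Appendix XI) asks TAU physicians to judge how useful the test result would have been. No order of completion is given.
- **Analysis.** SAP 2.1.3 and 2.1.4 list Month 12 comparisons, and SAP 5.2 compares congruence with TAU at every time point. Protocol 8.2.3 compares 1-year costs and outcomes. The SAP's only unblinding rule (3.2.1) stops at Week 8. No rule covers TAU data collected after release.

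**The concern.** The long-term comparison is meant to set guided care against usual care. If the TAU clinician can read the report before Visit 8 and act on it, part of the TAU arm may be guided when Month 12 is measured. If the participant hears the result first, the self-rated scales at that visit are no longer blinded.

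The issue is the content of the report. Clinicians know the allocation from randomization by design (13.0), and that is not in question.

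At stake are the Month 12 symptom, response and remission results, maintenance of response or remission to 12 months (Protocol 8.2.1 viii), Month 12 congruence, Month 12 safety and tolerability, and the last weeks of the 1-year costs.

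**Working it through.** The documents give no exposure figure to reproduce. The check is a timeline, followed by a reading of which outcomes fall inside it.

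**Inputs**
- Earliest release: 28 days before 12-month completion (Protocol 1.3, 7.1.3).
- Visit windows: Month 9 ±14 days, Month 12 ±21 days (9.7).
- Assumption: 12 months = day 365, so Month 9 = 9/12 × 365 = 273.75, taken as day 274.
- Completion at 12 months is not defined. Reading A counts back from the actual visit; reading B counts back from day 365.
- The end of costing is not defined either, so both the visit and day 365 are shown. The second is plausible because study data are to be "linked via health card number, encrypted at ICES, to the ICES administrative databases", a source that does not stop at the visit.

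**Timeline**
1. Visit 8 window: 365 − 21 = day 344 to 365 + 21 = day 386, which is 43 days.
2. Earliest release: A, 344 − 28 = day 316; B, 365 − 28 = day 337.
3. Latest Month 9 contact: 274 + 14 = day 288. Margin to the earliest release: 316 − 288 = 28 days (A) or 337 − 288 = 49 days (B). Month 9 and everything before it are clear.
4. Clinician access before the assessments: A, 0 to 28 days. Under B the maximum is visit day − 337, that is 7 days (visit on day 344), 28 (day 365) or 49 (day 386). The minimum is 0 in both, since 28 days is only the earliest release.

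**Maximum exposed costing days**

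| Costing ends | Reading A | Reading B |
|---|---|---|
| At the visit | 28 | 386 − 337 = 49 (49/386 = 12.7%) |
| Day 365 | 365 − 316 = 49 (49/365 = 13.4%) | 365 − 337 = 28 (28/365 = 7.7%) |

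**Scale of the window.** For eligibility the protocol says "Inadequate response is defined as inadequate efficacy after 6 weeks of a psychotropic treatment", that is 42 days. Reading A never reaches 42. Reading B does so only for visits from day 337 + 42 = 379 to day 386, 8 of the 43 possible days. This gives context only; it is not a threshold for an effect.

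**Which outcomes can move**
- *Congruence* is the most direct, because it records whether prescribing follows the report. Under SAP 7.4 a patient is congruent only if no red-category drug is prescribed, so only incongruent TAU patients can move towards congruence.
- *Symptoms* need early release, an unscheduled contact, a report-driven change and a response within weeks. The central HAM-D17 raters are blinded.
- *Side effects* can register sooner: FIBSER asks about the past week.
- *Self-ratings* could be touched by participant knowledge alone.
- *Direction.* Prescribing bias in efficacy runs towards no difference if the test helps. For side effects, and for self-ratings given with knowledge of the report, the direction cannot be told from the documents.

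**The case against.** The strongest reply is that the closing sentence of 7.1.3 is the operative definition of the arm and so forbids use of the report throughout. On that view early release only lets the clinician prepare for the visit or for the PIP-FQ item. The disclosure clause most naturally attaches to completion, section 9.7 puts disclosure at the Month 12 visit, and section 13.0 keeps the patient blinded with no end date. Nothing shows that early release or report-driven prescribing occurs, and the primary outcome is untouched.

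Much of this is fair. A benign purpose is plausible, and disclosure at the visit is the likelier reading. But the closing sentence of 7.1.3 is drawn as a consequence of a rule that itself allows earlier release, and it is not worded as a restriction on use. No section limits what the clinician may do with the report once it is held. Disclosure at the visit still leaves open whether it precedes the self-ratings.

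Four narrower points also stand. The six-week figure is an eligibility definition, and the trial itself measures HAM-D17 at Week 4. The 49-day figures are extremes. Medication changes and participant disclosure are already recorded. The missing Month 12 definition of congruence in SAP 7.4 affects all arms and other visits, so it is a separate gap and not evidence of contamination.

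**Conclusion.** The concern holds as a design weakness limited to Month 12 and the last weeks of the 1-year costs. The documents allow the TAU clinician 0 to 28 days with the report before assessment (reading A) or 0 to 49 days (reading B), and they do not secure participant blinding up to the Month 12 ratings. These figures rest on 12 months being day 365 and on visits falling within their windows. How often reports would be released early or acted on is not given, so no bias size is claimed. The Week 8 primary analysis, Week 12, Month 6 and Month 9 are not affected. The point should be corrected, but it does not threaten the main conclusion of the trial.

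**What to change.** **Protocol.** Reconcile 1.3, 7.1.3 and 9.7 so that the TAU report is released to the clinician, and disclosed to the participant, only after all Month 12 assessments (including the central HAM-D17) and current medication are recorded. Complete the PIP-FQ item that needs the report last. In the guided arms "results are returned via the GeneSight clinician portal to the treating clinicians", so a portal release rule can enforce this for TAU. Log TAU release and view dates; SAP 3.2.1 already uses view dates for GEN and E-GEN. State the end date of costing. Access before assessment then falls to 0 days. If costing runs to day 365, up to 365 − 344 = 21 days (21/365 = 5.8%) can remain exposed and should be reported.

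**SAP.** Define Month 12 congruence in 7.4 from medication recorded before release.

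**Patients already past this point.** Report how many TAU Month 12 assessments followed release, and the interval. Describe medication changes after release, but do not use them to define a comparison, and do not exclude TAU data collected after release. Beside Month 12, show the last unexposed time point for each scale:
- Month 9: HAM-D17, HAM-D6, EQ-5D-5L, medication and BARS.
- Month 6: SF-36.
- Week 12: QIDS-SR16, PHQ-9, GAD-7, CGI, UKU, FIBSER and weight. This is a distant comparator and cannot separate contamination from the ordinary course of illness.

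**Cost.** A minor amendment, a release rule and logged dates; no more patients. TAU clinicians may get the report up to about four weeks (A, 28 days) or seven weeks (B, 49 days) later than now allowed. Visit 8 is longer, because the report is read and explained after the assessments. If the central HAM-D17 falls on another day, disclosure follows the visit and may need a further contact.

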7.2 Modifications

At any time point, clinicians can modify a participant's medication based on their clinical judgment. Any switch or change in medications will be recorded on the CRF accordingly.

Women of childbearing age are advised to use a method of birth control during the course of the study. If they intend to get pregnant during the course of the study, then they should advise their primary care physician and/or psychiatrist to ensure that the pharmacotherapy being prescribed can be assessed for safety in pregnancy.

7.3 Concomitant Care

During the study, patients will be allowed to use concomitant medications at the Investigators' discretion. The dose and dose regimen of concomitant medications will be recorded on the CRFs.

8.0 OUTCOMES

8.1 Primary Outcome Measure

8.1.1 17-Item Hamilton Depression Scale (HAM-D₁₇)

The primary outcome will be the mean change in the HAM-D₁₇ score between baseline and 8 weeks. The HAM-D₁₇ assesses mood, feelings of guilt, insomnia, agitation or retardation, anxiety, weight loss and somatic symptoms(14-16) (see Appendix II).

8.2 Secondary Outcome Measures

8.2.1 Clinical Outcome Measures of MDD Symptoms and Medication Side Effects

i. 16-Item Self-Report Quick Inventory of Depressive Symptomatology (QIDS-SR16)

The QIDS-SR16 is a patient reported measure designed to assess the severity of depressive symptoms(17, 18). The scale assesses the nine DSM-IV criteria symptom domains for major depression: sad mood, concentration, self-outlook, suicidal ideation, involvement, energy/fatigability, sleep disturbance (4 items: initial, middle, late insomnia, and hypersomnia), appetite/weight increase/decrease (4 items), and psychomotor agitation/retardation (2 items) (see Appendix III).

ii. 9-Item Patient Health Questionnaire (PHQ-9)

The PHQ-9 consists of nine questions, rated 0–3 according to the increased frequency of difficulty experienced in each area covered. Scores are self-rated by patients, with a possible range of 0–27, are summed and can then be interpreted as follows: no depression (0), minimal (1–5), mild (6–9), moderate (10–14), moderately severe (15–19), or severe (>20) depression (see Appendix IV).

iii. Generalized Anxiety Disorder 7-Item (GAD-7) Scale

The GAD-7 is a brief measure of symptoms of anxiety, based on diagnostic criteria described in DSM-IV(19). It consists of seven questions and is calculated by assigning scores of 0, 1, 2, and 3, to the response categories of “not at all”, “several days”, “more than half the days,” and “nearly every day,” respectively (see Appendix V).

iv. Clinical Global Impression (CGI)

The Clinical Global Impression Scale (CGI) is a brief clinician-rated instrument that consists of three different global measures (see Appendix VI):

- Severity of illness: overall assessment of the current severity of the patient's symptoms (CGI-S);
- Global improvement: overall comparison of the patient's baseline condition with his current state (CGI-I);
- Efficacy index: overall comparison of the patient's baseline condition to a ratio of current therapeutic benefit and severity of side effects (CGI-EI).

v. Changes to initial prescribing based on availability of pharmacogenomic data

The influence of pharmacogenomic data on a physician's initial prescription for both GEN and E-GEN will be evaluated by documenting the psychotropic medication prescribed before the availability of the pharmacogenomics data. This will be compared to changes (if any) to the physician's prescription when pharmacogenomics data becomes available.

vi. Response Rates to Psychotropic Medication

A responder is defined as a participant who satisfies the following criteria:

- HAM-D₁₇: a 50% change from baseline in total scale score;

vii. Remission Rates

A remitter is defined as a participant who satisfies the following criteria:

- HAM-D₁₇ ≤ 7;

viii. Time to response or remission

Time to response or remission of depressive symptoms over 8 weeks and 12 weeks, and maintenance of response/remission up to 12 months as measured by the HAM-D₁₇.

ix. Udvalg for Kliniske Undersogeler (UKU) Side Effect Rating Scale

The UKU side effect rating scale, which is available as a patient self-rated assessment, is a comprehensive scale designed to assess the side effects in patients treated with psychotropic medications (see Appendix VII).

x. Frequency, Intensity, and Burden of Side Effects Ratings (FIBSER)

The FIBSER is a reliable and valid self-rated global measure of these three domains of side effects (frequency, intensity, and burden) in a population receiving treatment for depression (see Appendix VIII).

xi. Weight Gain

The side effect of AIWG will be evaluated by measuring study patients' weight and waist-to-hip ratio at baseline and at every visit.

xii. Medication Compliance

Medication compliance or adherence will be evaluated using two validated questionnaires, the Morisky 8-item medication adherence scale and the Brief Adherence Rating Scale (BARS), as well as prescription filling frequency between study visits to evaluate persistence and to validate costs of medication use(20-24).

